3.2 Rationale for Study Design and Control Group

The dose of NE3107 to be used in this study is 20 mg BID. Nonclinical safety studies and prior clinical trials have not identified a toxicity that supports the need for exploration of dose response. In vitro data indicate NE3107 is active at low nanomolar concentrations. NE3107 dose response for anti-inflammatory and insulin sensitizing activity was not statistically resolved between 2, 5 and 10 mg BID in impaired glucose tolerance subjects in trial HE3286-0102, and neither preclinical data, nor available clinical information suggest an ordered dose response relationship across exposure on key indices of glycemic control and insulin sensitivity. There has been no indication that NE3107's anti-inflammatory activity could be increased with higher exposures. NE3107 pharmacokinetics have high standard deviations for maximum serum concentration (C_{max}) and daily area under curve (AUC), which raise the concern for drug holiday or suboptimal trough plasma concentrations in participants with the lowest exposure. The dose of 20 mg BID is expected to increase the lowest expected C_{max} and AUC values to within 1 standard deviation below the average values for 10 mg BID, with trough values greater than 1 ng/mL.

3.3 Study Duration and Dates

The proposed participant recruitment start date will begin on 15 January 2022 and end on 31 January 2022. The recruitment period of 2 weeks, active treatment intervention period of 3 months, and final follow-up period of 2 weeks yields an expected 4-month study duration.

The actual overall study duration, start date and end date may vary depending on participant recruitment.

4 STUDY POPULATION SELECTION

4.1 Study Population

Number of Participants

Approximately 25 participants are expected to be enrolled in this Phase II trial to evaluate longitudinal findings from multimodal MRI among the population that is being studied.

Gender of Participants

The gender distribution for this study will aim for a ratio of 50:50 men to women. This is to ensure that both men and women benefit equally from any potential efficacy of NE3107 in treating dementia and that neither men nor women are disproportionately burdened by any tolerability issues. Women who are pregnant, who may become pregnant, or who are breastfeeding will not be included in the study.

Age of Participants

The ages for the participants in this study will range from 50-89 years old. This age range was selected based on the fact that degenerative conditions that result in cognitive change occur in middle and late life.

4.2 Inclusion Criteria

In order for a subject to be considered for this study, the following criterion is required:

- Diagnosis of cognitive decline due to degenerative dementia
- Age within range of 50-89 years old
- QDRS score ranging from 1.5-12.5, with a converted Clinical Dementia Rating (CDR) score of 0.5 (mild cognitive impairment) to 1 (mild dementia)

The QDRS scale will be given to all patients; a cutoff range for QDRS scores has been specified as 1.5-12.5 to qualify patients with a clinical dementia score (CDR) of 0.5 to 1.

4.3 Exclusion Criteria

In order for a subject to be considered for this study, he/she may NOT have any of the following:

- Subjects with contraindications for lumbar puncture, such as bleeding abnormalities, use of anticoagulant medications, and local skin or spine abnormalities. *See Section 6.6.1 “Laboratory Parameters,” page 26.*

- Subjects with contraindications to magnetic resonance imaging (MRI) acquisition, including patients with non MRI-compatible pacemakers, defibrillators, or other implanted electronic devices.
- Women who are pregnant, who may become pregnant, or who are breastfeeding
- Reversible causes of cognitive impairment that explains the clinical status entirely, such as hypothyroidism, depression
- Advanced stages of any terminal illness or any active cancer that requires chemotherapy
- History of breast cancer
- Women with child-bearing potential who are not willing to use a double-barrier birth control method
- Males not willing to use a double-barrier birth control method with female sex partners with child-bearing potential
- Individuals with hepatic impairment as defined by:
 - Alanine aminotransferase (ALT) lab values $>3x$ the upper normal limit (UNL)
 - Aspartate aminotransferase (AST) lab values $>3x$ UNLOR
 - History of clinically significant liver disease in the Principal Investigator's medical judgment
- Individuals with renal impairment as defined by Creatinine clearance (Cockcroft-Gault formula) of <45 mL/min.

5 STUDY TREATMENT(S)

5.1 Description of Treatment(s)

5.1.1 Study Drug

NE3107 is an investigational orally bioavailable, blood-brain barrier permeable anti-inflammatory agent with a new mechanism of action targeting multiple mechanisms of pathology in Alzheimer's disease. NE3107 is an uncharged, low molecular weight molecule, poly-hydroxylated synthetic derivative of the C-19 adrenal steroid series. *In vitro* studies have been conducted to measure membrane transport, active efflux/P-gp interaction, hepatic stability, CYP inhibition, and CYP induction.

5.1.2 Placebo or Control

All participants will receive the study drug; this study will utilize no placebo group.

5.2 Treatment(s) Administered

The drug under investigation is NE3107 (17a-ethynyl-androst-5-ene-3b,7b,17b-triol). NE3107 is formulated with common excipients used in oral medications in #2 hard gelatin capsules. The capsules are designed for oral administration. The dose of NE3107 (Biovie, inc.) is 20 mg twice daily (BID) approximately 12 hours apart, for the duration of 3 months. Study drug will be dispensed and monitored by the Sponsor.

5.3 Selection and Timing of Dose for Each Participant

The dose of NE3107 (Biovie, inc.) is 20 mg twice daily (BID) approximately 12 hours apart. The dose will be stable for the duration of the study intervention, and will be the same for all participants.

5.4 Method of Assigning Participants to Treatment Groups

All participants will receive active study drug at the same dosage.

5.5 Blinding

No blinding procedures will be utilized.

5.6 Concomitant Therapy

Concomitant medications will be considered any therapies that the patient begins/continues taking from the time point of 30 days prior to first dose of NE3107. Concomitant medications will be stabilized for 30 days prior to entry in the study protocol. There are no pharmacologically or toxicologically important NE3107 metabolites for consideration in drug exposure rationale, but memantine and acetylcholine esterase inhibitors, galantamine, donepezil and rivastigmine, are permitted as co-medications in the proposed study. Memantine and rivastigmine do not have appreciable interactions with hepatic CYP

enzymes, so they do not factor into drug-drug PK interactions. Donepezil is predominately metabolized by CYP2D6, but is also metabolized by CYP3A4. NE3107 is also metabolized primarily by CYP3A4. In conclusion, no drug-drug PK interactions with co-medications memantine, donepezil, galantamine and rivastigmine are expected with the proposed dose of 20 mg BID. As noted in the exclusion criteria, patients with contraindications for lumbar puncture (such as bleeding abnormalities requiring the use of anticoagulant medications) will not be permitted into the study. Additionally, participants with any active cancer requiring chemotherapy will not be permitted to take part in the study.

5.7 Restrictions

5.7.1 *Prior Therapy*

There are no restrictions of entry to the study based on prior therapy.

5.7.2 *Fluid and Food Intake*

Patients will be required to obtain bloodwork having fasted for a period of time no less than 8 hours. There are no other fluid or food intake restrictions during the course of the study.

5.7.3 *Participant Activity Restrictions*

The participant will have no activity restrictions related to study involvement.

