2 STUDY OBJECTIVES

2.1 Primary Objective(s)

Primary endpoints will involve a comparison of neurophysiological health as evaluated by multi-modal brain MRIs obtained at baseline and post-intervention termination (3 months). Specifically, multi-modal MRI endpoints will include: (1) An increase or stabilization in glutathione levels (as measured by magnetic resonance spectroscopy, MRS) compared to baseline. Patients with cognitive decline often show characteristic change in MRS or volumetric evaluation compared to age-matched controls (Kuhn et al. 2021); (2) Stabilized and/or improved dendritic density compared to baseline (as measured by diffusion tensor imaging, DTI-NODDI); (3) Enhancement of arterial signal compared to baseline (as quantified by arterial spin labeling, ASL). Patients with cognitive decline often have decreased perfusion in temporal parietal or frontal regions of the brain with ASL perfusion (Kuhn et al. 2021); (4) increased functional connectivity of the nucleus basalis of Meynert (NBM) with both hippocampi as well as between both hippocampi compared to baseline, as visualized by seed analysis of blood-oxygen level dependent (BOLD) imaging as well as (5) increased neurovascular coupling as visualized by BOLD compared to baseline.

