Collected at Weeks 2, 4, and 8:

- Amylase
- Lipase
- Potassium
- Calcium
- Complete Blood Count (CBC) with Differential

- Hemoglobin A1c
- Glucose
- Alanine aminotransferase (ALT;
SGPT)
- Aspartate aminotransferase (AST;
SGOT)
- Creatine Phosphokinase
- Cholesterol total (Fasting)
- HDL (Fasting)
- LDL (Fasting)
- Triglycerides (Fasting)

Collected Prior to Lumbar Puncture
Procedure:

- Prothrombin time
- International Normalized Ratio
- Partial thromboplastin time
- Platelet count

6.6.2 *Sample Collection, Storage, and Shipping*

After screening, laboratory orders will be written by the study physician which can be taken to any Quest Diagnostics, LabCorp, or any other clinical laboratory. Additional serum will be drawn at the primary study site and sent for analysis to Prodrome Sciences ([name]). Samples will be shipped on ice and labeled adhering to federal biological substance shipping regulations.

6.7 *Dispensing Study Drug*

The Manufacturer will supply sufficient quantities of the study formulation for the following: (1) completion of this study and (2) retention, as per applicable regulations. All drug supplies provided for this study will be stored in a secure area with restricted access, under controlled storage conditions described in the product package labelling, unless otherwise instructed per protocol.

Records will be made of receipt and dispensing of NE3107 supplied. It is the responsibility of the Manufacturer to ensure that all drug supplies provided for the study are manufactured under current Good Manufacturing Practices (cGMP) and are suitable for human use.

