7 STUDY ACTIVITIES

7.1 Screening Visit & Baseline Measure Collection (Days -10 to -1)

Study Screening may take place during an initial visit with study staff to obtain the following assessments, which will be recorded in participant's source documentation/medical record and on the Case Report Form (CRF):

- Participant ID number generation
- Demographic information
- Medical history
- Vital signs
- Height, weight, and calculation of BMI
- Prior/concomitant medications (must be stabilized for 30 days prior to study entry)
- Quick Dementia Rating Scale (QDRS)
- Clinical Dementia Rating (CDR) score, derived from QDRS
- Confirming eligibility (no exclusionary criteria are met)

Baseline measure acquisition may take place over the subsequent 9 days prior to starting the active study intervention, which will include the following:

- Lumbar puncture to test for AB42 and Tau protein levels
- APoE genotyping
- Advanced brain MRI
 - T1, T2, SWI, Neuromelanin, BOLD, ASL perfusion, DTI-NODDI, MRS of the precuneus
- Cognitive examination including:
 - Montreal Cognitive Assessment (MoCA)
 - Mini-mental Status Examination (MMSE)
 - Alzheimer's Disease Assessment Scale (ADAS-Cog12)
- Blood tests for:
 - Complete blood count + diff
 - Creatinine clearance
 - Thyroid hormone panel
 - Electrolytes
 - Inflammatory markers (hsCRP, TNF α , CD4, CD8, absolute neutrophils)

- Quantitative immunoglobulins
- Total and direct bilirubin
- Hemoglobin
- ProdromeScan blood test for:
 - Phosphatidylethanolamines
 - Choline
 - Mitochondrial function

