7.5 Follow-up Visit (Day 90 ± 15)

At the 3-month follow-up visit, the following assessments will be performed and recorded in the participant's source documentation/medical record and on the CRF:

- Vital signs
- Weight
- Concomitant medications
- AEs
- Quick Dementia Rating Scale (QDRS)
- Clinical Dementia Rating (CDR) score, derived from QDRS
- Lumbar puncture to test for AB42 and Tau protein levels
- Advanced brain MRI
 - T1, T2, SWI, Neuromelanin, BOLD, ASL perfusion, DTI-NODDI, MRS of the precuneus
- Cognitive examination including:
 - Montreal Cognitive Assessment (MoCA)
 - Mini-mental Status Examination (MMSE)
 - Alzheimer's Disease Assessment Scale (ADAS-Cog12)
- Blood tests for:
 - Complete blood count + diff
 - Creatinine clearance
 - Thyroid hormone panel
 - Electrolytes
 - Inflammatory markers (hsCRP, TNF α , CD4, CD8, absolute neutrophils)

- Quantitative immunoglobulins
- Total and direct bilirubin
- Hemoglobin
- ProdromeScan blood test for:
 - Phosphatidylethanolamines
 - Choline
 - Mitochondrial function

Note: NE3107 was not teratogenic in rat and rabbit safety studies. Sexually active male and female patients on study should continue using barrier method contraception for 72 hours (three days) after the last dose of NE3107 (terminal plasma t1/2 6-8 hours). The outcome of any pregnancy conceived by a patient on study will be followed to term and the results (normal or detailed description of abnormalities) will be collected as part of the study data and reported to the primary IND holder (Biovie, Inc.).

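### No rule keeps caffeine, meals and time of day the same for the two MRI scans, so the ASL and BOLD primary endpoints carry avoidable noise and possible, though not demonstrated, bias

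*Combined protocol and SAP*

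**What the plan says.** Section 5.7.2 has one dietary requirement, and it concerns blood tests: "Patients will be required to obtain bloodwork having fasted for a period of time no less than 8 hours". It then closes the subject: "There are no other fluid or food intake restrictions during the course of the study". Section 5.7.3 adds: "The participant will have no activity restrictions related to study involvement".

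The MRI text lists sequences (Sections 6, 7.1 and 7.5) and processing steps (Section 9.5.1). It sets no time of day, fed or fasted state, or caffeine rule for either scan. By contrast, Section 6.4 keeps the device and the arm constant when blood pressure and heart rate are measured.

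Section 2.1 names five primary MRI endpoints. Three are ASL perfusion, BOLD functional connectivity and "increased neurovascular coupling as visualized by BOLD compared to baseline". All compare one baseline scan with one scan at three months. Section 5.1.2 confirms that there is no placebo group, and Section 9.2 plans for at least 20 completers.

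On scheduling, Section 7.1 says: "Baseline measure acquisition may take place over the subsequent 9 days prior to starting the active study intervention". Section 7.5, headed Day 90 ± 15, says: "At the 3-month follow-up visit, the following assessments will be performed and recorded". Under Section 6.6.2, laboratory orders are written by the study physician, "which can be taken to any Quest Diagnostics, LabCorp, or any other clinical laboratory".

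**The concern.** ASL measures perfusion, and BOLD depends on blood oxygenation and flow. Anything that changes cerebral blood flow on the day of the scan can therefore enter these endpoints. Section 5.7.2 is not merely silent. It affirmatively excludes further food or fluid restrictions, so a scan-day caffeine or meal instruction from the imaging staff would contradict the protocol as written.

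The within-person design relies on the two scans differing only by three months of treatment and disease course. If pre-scan state varies at random between the scans, it widens the spread of about 20 paired differences. If it varies in a common direction, the mean change moves, and no control arm is available to subtract that movement. An upward shift in flow matters most, because the plan treats higher ASL signal as success and Section 9.5.1 also counts stabilisation in the temporal-parietal comparison. The named covariates are age, sex and education, other demographics and, for BOLD, neuropsychological assessment. None describes the state at scanning.

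**Working it through.** **The plan's own figure.** Section 9.2 inflates 20 completers for 20% attrition: 20 / (1 - 0.20) = 25. This reproduces. The 80% power behind the 20 cannot be reproduced, because no effect size, standard deviation, test or sidedness is stated.

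**Illustration 1: shift in mean flow.** Assumptions, not in the documents: caffeine lowers resting flow by a fraction d between 0.15 and 0.30; 5 of 20 participants are caffeinated at baseline and not at follow-up; the other 15 are caffeine-free at both; the drug has no effect. Set caffeine-free flow to 1.

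- Baseline mean = 1 - (5/20)d = 1 - 0.25d. Follow-up mean = 1.
- Apparent rise = 0.25d / (1 - 0.25d).
- d = 0.15: 0.0375 / 0.9625 = 3.9%.
- d = 0.30: 0.075 / 0.925 = 8.1%.

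If five other participants switch the opposite way, both means equal 1 - 0.25d and the mean does not move. The individual changes are then +d for five, -d for five and 0 for ten. Their variance (divisor 20) is (10/20)d², so the standard deviation is 0.707d: 10.6% to 21.2% of caffeine-free flow, as pure noise.

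**Effect of the grey-matter ratio.** Section 9.5.1 examines CBF relative to mean grey-matter signal. If regional flow r and grey-matter flow g both fall by the fraction d, then r(1 - d) / [g(1 - d)] = r/g, and the shift disappears. If they fall by different fractions d_r and d_g, the ratio is multiplied by (1 - d_r)/(1 - d_g), and a regional artefact stays. The documents give no basis for a figure here. The later temporal-parietal comparison with a normative database does not restate the ratio, and the BOLD endpoints have no counterpart to it.

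**Illustration 2: cost without a caffeine figure.** Use a paired t-test, n = 20, two-sided 0.05, 19 degrees of freedom, noncentrality δ√20. With two time points and no covariates, the planned repeated-measures ANOVA is the same test. Correction for multiple comparisons is left out.

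Systematic shift with no drug effect:

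| Shift (SD of change) | Chance of a significant result |
|---|---|
| 0 | 5% |
| 0.1 | 7.1% |
| 0.2 | 13.6% |
| 0.3 | 24.7% |
| 0.5 | 56.5% |

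Random differences only. The effect detectable with 80% power is δ = 0.66; if scan state inflates the change-score variance by a factor 1 + v, the effective size is 0.66/√(1 + v):

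| Added variance v | Effective size | Power |
|---|---|---|
| 0 | 0.66 | 80% |
| 25% | 0.59 | 71% |
| 50% | 0.54 | 63% |
| 100% | 0.47 | 51% |

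The documents do not say which rows apply.

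**The case against.** The strongest reply is that nothing in the protocol makes the two scans differ in a consistent direction. A reader might infer that baseline procedures are spread over nine days while follow-up puts scan, fasting bloods and lumbar puncture into one visit, so that participants are scanned fed at baseline and fasted, caffeine-free or just after CSF removal at follow-up. The text does not support that. Bloods may be drawn at any outside laboratory at both time points, so the fast is not tied to the scan day. Follow-up has its own ±15-day window, and Section 3.3 allows two weeks for it. The assessment lists are much the same at both ends. This stands: systematic bias is possible, not shown.

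A reader might also infer an effect from a preceding lumbar puncture or from when a permitted cholinesterase inhibitor is taken. The documents say nothing about either altering ASL or BOLD, and no range can be given from them. Concomitant medication must be stable for 30 days before entry and changes are documented, which narrows the medication question without fixing intake time. The Appendix 1 Schedule of Events is not in the available text and may fix the order of MRI and lumbar puncture, so that order cannot be called an omission.

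The ratio to grey matter is a real safeguard for ASL against a uniform shift, so 3.9-8.1% is not an estimate of error in the planned ASL result. Finally, the missing control arm already prevents attribution to the drug, and standardised scans do not cure that. This bears on the weight of the point. It is no reason to leave avoidable variation in the primary measurements.

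**Conclusion.** The point holds as a matter of measurement control. Section 5.7.2 excludes any dietary preparation for the scans, and nothing in the MRI text requires like-for-like conditions. Differences in caffeine, meal state or time of day can therefore enter three of the five primary endpoints. The supported consequence is noise in about 20 paired changes; bias follows only if the differences happen to be systematic.

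The size is illustrative. The 3.9-8.1% rise in mean absolute flow rests on an assumed 15-30% caffeine effect and 5 of 20 participants switching in one direction, before the grey-matter ratio. The false-positive and power figures rest on assumed shifts and added variance. That meals and time of day matter for these signals is likewise an assumption. The exposure is greater for BOLD than for ASL, because the ratio protects only ASL and only against a uniform shift. This is a cheap improvement worth making before the first scan, since unrecorded scan conditions cannot be recovered reliably later. It is not a fatal flaw.

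**What to change.** 1. Amend Section 5.7.2. Keep the fast for blood tests and replace the closing sentence with a rule such as: *each participant's two MRI examinations will be done at the same time of day and in the same fed or fasted state, with no caffeine for a fixed, stated number of hours before each scan.*
2. Add three fields to the scan form: last caffeine, last meal and last co-medication intake. The medication field is a record only; how any medication is taken does not change.
3. Prespecify a repeat of the ASL and BOLD analyses without pairs scanned under different conditions, and report how many pairs were dropped.
4. Unless Appendix 1 already does so, state in Sections 7.1 and 7.5 the same order of MRI and lumbar puncture at both time points.

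Cost: protocol wording, an appointment instruction, three form fields and one sensitivity analysis. The downside is slightly less scheduling flexibility and a caffeine-free period before two scans. The sensitivity analysis loses precision if many pairs are mismatched; dropping 5 of 20, for example, leaves 15.

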5.8 Treatment Compliance

Participants / primary caregiver / study partner will be instructed to bring their unused investigational product (IP) to every visit. Compliance will be assessed by capsule counts. Details will be recorded in the case report form. All unused IP will be collected from the participant at V10/ET. Noncompliance is defined as taking less than 80% or more than 120% of the assigned dose during any outpatient evaluation period (visit to visit). Discontinuation for noncompliance is at the Investigator's discretion.

5.9 Packaging and Labeling

Each investigational study drug will be labeled (in English) with a statement indicating that the drug is an investigational drug to be used only by a Qualified Investigator and will include but not limited to: Drug Name, Strength, Protocol Number, Sponsor's Name and Address, the recommended storage conditions for the drug, Expiry/Retest Date (when available) and Lot/Batch Number.

